- (2) Any condition or criteria, including acute or chronic clinically significant abnormality that in the opinion of the investigator might compromise the wellbeing of the participant or interfere with the outcome of the study

For participation in mass vaccination campaigns (with full or fractional dose PCV10)

Inclusion criteria:

- (1) Aged 1-9 years
- (2) Residing in the villages included in the study and allocated to vaccination
- (3) Head of the household or main caretaker provides consent for the child to be vaccinated

Exclusion criteria:

- (1) Hypersensitivity to any component of the vaccine, including diphtheria toxoid
- (2) Vaccination with a PCV vaccine within the previous 4 weeks, as there should be a minimum of 4 weeks between doses
- (3) Moderate or severe febrile illness (temperature $\geq 39^{\circ}\text{C}$) is a temporal contraindication and the child should not be vaccinated until improvement
- (4) Any condition or criteria, including acute or chronic clinically significant abnormality that in the opinion of the clinical staff might compromise the wellbeing of the volunteer

Study Type

Phase IV cluster-randomized controlled trial

Date of First Enrolment

November 2021

Target Sample Size

63 clusters with a total population between 500 and 4000 will be randomized in a 3:3:1 ratio to receive either (1) mass campaigns targeting children aged 1-9 years with a single full dose of PCV10, (2) mass campaigns targeting children aged 1-9 years with a single fractional (1/5) dose of PCV10, or (3) no mass campaigns (control arm). It is estimated that approximately 32 000 children will be targeted by the campaigns.

Cross-sectional surveys conducted at baseline prior to the vaccination campaign, and approximately 6 months after the vaccination campaign, will collect nasopharyngeal swabs from children aged 1-9 years. Simple random sampling will be used to select 36 households from each of the 63 clusters. One child aged 1-9 will be randomly selected from each household to participate. A total of 2268 children will be targeted in each survey.

Recruitment Status

Not yet recruiting

Primary Objective

To evaluate whether a mass vaccination campaign targeting children approximately 1-9 years of age with a full dose of PCV is superior to the absence of vaccine in reduction of VT carriage prevalence at 6 months post-campaign, and subsequently to evaluate if a single 20% dose of PCV is non-inferior to a full dose.

Secondary Objectives

- To measure the age-stratified prevalence of NP carriage of *S. pneumoniae* in children 1-9 years of age in the study area.
- To determine the effect of a mass vaccination campaign with one full dose of PCV in children 1 to 9 years of age on VT pneumococci carriage 6 months after vaccination
- To assess the occurrence of adverse events (AE) during 7 days and serious adverse events (SAE) during 28 days after administration of fractional and full doses of PCV.
- To model the potential effect of fractional dose PCV campaigns in other contexts using the results of the clinical trial.
- To develop recommendations on how a potential future fractional dose PCV mass campaign could be successfully planned, communicated, delivered and integrated into national immunization programmes using qualitative analysis.

Data Safety and Monitoring Board

To be named

3 Abbreviations

AE	Adverse Event
CRF	Case Report Form
DSMB	Data and Safety Monitoring Board
EC	Institutional Ethical Committee
ERC	Ethics Review Committee
GCP	Good Clinical Practice
ICF	Informed Consent Form
ICH	International Conference on Harmonization
IRB	Institutional Review Board
ISF	Investigator site file
LMIC	Low and middle-income countries
MOH	Ministry of Health
MSF	Doctors Without Borders
NP	Nasopharyngeal
NRA	National regulatory authority
PI	Principal Investigator
PIS	Patient information sheet
SAE	Serious Adverse Event
SII	Serum Institute of India Pvt. Ltd
SSL	Secure Sockets Layer
SOP	Standard operating procedures
SUSAR	Suspected unexpected serious adverse reaction
VT	Vaccine-type
WHO	World Health Organization

4 Background

In 2015, there were an estimated 8.9 million cases (uncertainty range 7.7-10.6 million) of clinical pneumococcal pneumonia globally, with 2.4 million cases estimated in Africa alone (uncertainty range 2.1-3.1 million) (1). These figures represent a global reduction of 37% from 14.2 million cases (12.3 million–16.9 million) in 2000. However, pneumococcal disease continues to be a leading cause of severe disease and death representing 10% of all death in children under 5 years of age (1). These deaths occur disproportionately in low- and middle-income countries (LMICs), with approximately 50% of global pneumococcal deaths estimated to occur in 4 countries: India, Nigeria, Pakistan and the Democratic Republic of Congo (1).

Streptococcus pneumoniae is part of the normal bacterial flora in the nasopharynx (NP) (2). Colonization with *S. pneumoniae* is generally asymptomatic, but in some cases it spreads and causes disease, including sinusitis, otitis media, bacteraemia and meningitis, referred to as invasive pneumococcal disease (IPD) (3). It has been estimated that approximately 75% of cases of IPD, and 83% of cases of pneumococcal meningitis, occur in children <2 years, although these estimates may vary by country, study method and socio-economic status within countries (4). There are over 90 known pneumococcal serotypes identified throughout the world, but a small number are responsible for most severe disease (4). The pneumococci are easily transmitted from person to person, generally within families, from older to younger siblings and between households within communities (2). NP colonization generally occurs early in life (2), with some studies reporting a peak in children younger than 2 years of age (5). Studies have estimated NP carriage prevalence >70% among children <5 years in Kenya (6), The Gambia (7) and Uganda (8) in the period before introduction of pneumococcal conjugate vaccines (PCV).

PCVs were introduced in Africa from 2011 onwards with support from Gavi, the Vaccine Alliance. At present there are three PCVs that are WHO-prequalified: Synflorix™, a 10-valent vaccine (PCV10); Prevenar®, a 13-valent vaccine (PCV13); and the most recently prequalified PCV10, Pneumosil®. The vaccines contain different serotypes, though each includes serotypes most frequently responsible for severe disease, and are considered effective against pneumococcal disease (4,9). Vaccination with PCV has a direct effect reducing carriage amongst those vaccinated, but also has the capacity to reduce carriage amongst unimmunized populations by interrupting transmission (10). This indirect effect of vaccines that goes beyond individual protection is linked to the reduced exposure to *S. pneumoniae* vaccine serotypes (VT) in communities where a large proportion of the population have been vaccinated (10), i.e., herd protection.

To date, the majority of countries have introduced PCV into routine immunization programs (11). Following WHO recommendations, most LMICs have introduced the vaccine in a 3 dose schedule, starting at 6 weeks of age and with vaccine doses separated by 4 weeks (4). In settings with high disease burden and mortality, catch-up vaccination at the time of vaccine introduction has also been recommended to accelerate the impact of vaccination. Catch-up vaccination should ideally target children 1 to 5 years of age and should prioritize children <2 years of age (4). The WHO Framework for vaccination in humanitarian emergencies also recommends PCV mass campaigns following assessment of local epidemiology and other risk factors (12). In humanitarian emergencies, mass campaigns could rapidly establish direct and indirect protection when vulnerability is highest and routine health services are disrupted (13).

Coverage of PCV vaccination through routine immunization has been heterogeneous. Some countries achieved >80% coverage quickly after introduction of the vaccines and have been able to sustain this over time. Other countries, however, have difficulties and continue to have low coverage (<50%) years after vaccine introduction (14). Carriage studies conducted in LMICs with high vaccination coverage have shown some level of residual VT carriage. For instance, in Malawi, 7 years after the introduction of PCV13, VT carriage is reported at 16.6% VT amongst 3-5 years old vaccinated children (15). In a study conducted in Kilifi, Kenya, 5 years after PCV10 introduction, VT pneumococci is identified in 6% of children aged less than 5 years and 8% of infants (16). However, it has been considered that current vaccination strategies are unlikely to reduce this further (17). Further complicating this, although decreasing VT colonization with PCV decreases subsequent IPD, the exact nature of the relationship is not well-described, and a target threshold necessary to establish herd protection has not been established. Regardless, in countries with low vaccination coverage, the beneficial effects of PCVs have yet to be fully realized. Mass campaigns as a strategy to boost herd protection in areas of low routine vaccination coverage, could have a role in these different settings.

However, a barrier to PCV vaccination strategies is their cost. From 2001 to 2017, the cost to fully immunize a child in LMICs has increased from USD 1.00 to approximately USD 32.00¹, with vaccines against rotavirus and pneumococcal disease accounting for three quarters of the total cost of vaccinating a child (11). These high costs also impact considerations of PCV for mass vaccination campaigns (13).

5 Rationale

Vaccination campaigns targeting children up to 5 years of age, in addition to routine vaccination in infancy, have been shown to have an effect in the reduction of VT carriage and disease (18,19). However, the benefits of catch-up campaigns are reduced if they delay or affect coverage of routine vaccination activities, and if those in the catch-up age cohort have only moderate vaccine serotype carriage and disease (4). Moreover, there is limited evidence on the optimal deployment strategies for mass campaigns (4,13). Some programs, for instance, have used a single dose while others have considered that two PCV doses are needed for children 12-23 months of age (4). The target age group for mass vaccination has also varied. WHO recommendations for catch-up vaccination target children <5 years of age. However, this target has been questioned as there is no clear rationale for this limit (13). Whilst it has been considered that children <5 years of age usually bear the heaviest burden of pneumococcal pneumonia, this is not necessarily the case in all settings. In crisis situations or in settings with high prevalence of malnutrition, the high pneumococcal carriage prevalence is likely to extend to older age groups and vaccination of a larger age group might be needed to control VT circulation (13). Consequently, the inclusion of older children in campaigns might be beneficial in particular settings where older children contribute substantially to the transmission of pneumococci (18).

Niger introduced PCV13 into the routine vaccination program in 2014, with doses given at 6, 10, and 14 weeks of age, without catch-up campaigns. Administrative coverage with 3 doses was estimated to be 81% in 2019, however, coverage estimated directly in the Maradi region is considered to be

¹ Excluding HPV vaccine.

around 48%², suggesting a heterogeneity in the reach of the program. Currently, for Gavi-supported countries, such as Niger, PCV13 vaccine has a cost of US\$3 per dose. The most recently WHO prequalified PCV vaccine (Pneumosil®) has, however, the lowest price at US\$2 per dose. The vaccine cost is also far below current market prices offered by the other manufacturers for uses outside Gavi support (20). Consequently, as the overall cost to health systems is lower, this provides more opportunities to countries and organizations supporting countries on the choice of how to use the vaccine—Pneumosil® is a PCV10 manufactured by Serum Institute of India Ltd (SII), tailored specifically to African, Asian, and Latin American countries by including serotypes 6A and 19A, two serotypes available in PCV13 but not in the Synflorix™ PCV10 (21). Although Pneumosil® is a PCV10, which has fewer serotypes than PCV13, there is currently insufficient evidence to show any difference in impact between PCV10 and other PCV vaccines (4,9). Moreover, although product switching, in this case from PCV13 to PCV10, has not been recommended (4), a mass campaign would be directed to children older than the routine vaccination target group (infants), and for many this would be done years after they received their primary schedule.

Although a relatively low cost PCV (Pneumosil®) is currently available, mass campaigns targeting large age groups with a full dose of vaccine would require a large quantity of vaccine and might not be sustainable over time. Fractional dosing of licensed vaccines have been considered for situations of high vaccine costs and/or supply chain shortages (22). Fractional doses administered through the intradermal route have been assessed for several vaccines including influenza, rabies, hepatitis B, inactivated polio vaccine (IPV) (23) and through the standard subcutaneous route for yellow fever vaccine (24). Following available evidence, fractional doses of IPV, rabies and yellow fever vaccines are recommended by WHO and used routinely in several countries and for outbreak response (25,26). Data from the original dose-finding studies for a pentavalent PCV indicate that a dose as low as 1/4th of the current dose in PCV10 could elicit adequate immunogenicity (27). A non-inferiority trial of fractional doses of PCV10 and PCV13 is currently underway in Kenya (ClinicalTrials.gov Identifier: NCT03489018; PI [name]). Following this, fractional doses of PCV could be a solution to overcome the high PCV costs, increase vaccine access and expand vaccination benefits through alternative strategies.

This study aims to assess the impact of a mass campaign with a single, fractional dose of Pneumosil®, a PCV10, on VT carriage. A 20% fractional dose (1/5th) will be used as a practical formulation to prepare and administer. This study will assess whether the impact of a single fractional dose mass campaign on carriage is non-inferior to a single full dose mass campaign in a cluster randomized trial in a low coverage setting in Niger. The results would provide evidence of the population-level direct and indirect impact of fractional dose in older children which will be completed by mathematical modelling, to inform the policy debate regarding PCV dosing schedules in different contexts. This trial and the modelling exercises that follow, would allow for larger scale evaluation of fractional dose PCV strategies in multiple contexts.

² Administrative coverage from UNICEF Immunization data <https://data.unicef.org/topic/child-health/immunization/>
Actual coverage from MSF-Epicentre data.

6 Study Objectives

Primary objective

To evaluate whether a mass vaccination campaign targeting children approximately 1-9 years of age with a full dose of PCV is superior to the absence of vaccine in reduction of VT carriage prevalence at 6 months post-campaign, and subsequently to evaluate if a single 20% dose of PCV is non-inferior to a full dose.

Secondary objectives

- To measure the age-stratified prevalence of NP carriage of *S. pneumoniae* in children 1-9 years of age in the study area.
- To determine the effect of a mass vaccination campaign with one full dose of PCV in children 1 to 9 years of age on VT pneumococci carriage 6 months after vaccination
- To assess the occurrence of adverse events (AE) during 7 days and serious adverse events (SAE) during 28 days after administration of fractional and full doses of PCV.
- To model the potential effect of fractional dose PCV campaigns in other contexts using the results of the clinical trial.
- In the setting of a qualitative study, to develop recommendations on how a potential future fractional dose PCV mass campaign could be successfully planned, communicated, delivered and integrated into national immunization programmes using qualitative analysis.

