7.5.1 Inclusion and exclusion criteria

Households containing at least one member aged 1-9 years whose head of the household or main caretaker provides consent to participate will be eligible to participate.

To participate in the carriage surveys, children meeting the following inclusion criteria are eligible for enrolment:

- (4) Aged 1-9 years
- (5) Residing in the villages included in the study
- (6) Parent or caretaker provides informed consent for the child to participate in the study

Exclusion criteria for participating in the carriage survey will include the following:

- (3) Head or facial injuries that contraindicate nasopharyngeal swabbing
- (4) Any condition or criteria, including acute or chronic clinically significant abnormality that in the opinion of the investigator might compromise the wellbeing of the participant or interfere with the outcome of the study

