- 2) Select a child of the target age group for vaccination at random for nasopharyngeal swab. A short questionnaire will be used to collect the child's recent symptoms of an upper respiratory tract infection, including receiving any antimicrobials in the previous two weeks. If the selected child is absent from the household, a second attempt of inclusion will be made at another agreed upon time. In the rare event that the child is not eligible to participate another member will be randomly selected from the list. In the unlikely event that no child in the household is eligible to participate in the survey, the household will not be replaced.

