7.11 Randomization and blinding procedures

Following the results of the baseline survey, clusters will be randomized in a 3:3:1 ratio, with 27 clusters randomized to receive a campaign with the full dose, 27 clusters randomized to receive a campaign with the fractional dose and 9 clusters randomized to the control arm. Randomization will be stratified by proximity to nearest health center (<5 km vs. ≥5km). In the event of significant imbalance in carriage of VT pneumococci between clusters in the baseline survey, randomization will also be stratified by baseline prevalence. An equal or proportional number of clusters will be randomized to each study arm from each stratum.

The randomization list will be generated by an independent statistician with no other contact with trial participants.

Study implementation will be blinded to the extent possible. Vaccination nurses will not be blinded to the vaccine they are giving, but they will not communicate vaccine allocation to other members of the team or to participating villages. Villages randomized to the control arm will not receive any “dummy” intervention, so will not be blinded to their group allocation. The trial will be observer-blind in that personnel at KWTRP will be blinded to group allocation until after the completion of culture and serotyping in each survey.

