3.1.1.1 Inclusion and Exclusion Criteria

To participate in each cross-sectional surveys (baseline and post vaccination), one child per household will be randomly selected for the nasopharyngeal sampling if he is eligible for enrolment after meeting the following inclusion criteria:

- Aged 1-9 years
- Residing in the villages included in the study
- Parent or caretaker provides informed consent for the child to participate in the study

Exclusion criteria for participating in the surveys will include the following:

- Head or facial injuries that contraindicate nasopharyngeal swabbing
- Any condition or criteria, including acute or chronic clinically significant abnormality that in the opinion of the investigator might compromise the wellbeing of the participant or interfere with the outcome of the study

For mass vaccination campaigns, all children of the target age group for vaccination, for instance aged 1-9 years of age, residing in the study villages allocated to full or fractional dose arm will be targeted for vaccination.

Children meeting the following inclusion criteria will be eligible for vaccination:

- Aged 1-9 years
- Residing in the villages included in the study and allocated to vaccination
- Head of the household or main caretaker provides consent for the child to be vaccinated

Exclusion criteria for vaccination will include the following:

- Hypersensitivity to any component of the vaccine, including diphtheria toxoid
- Vaccination with a PCV vaccine within the previous 4 weeks, as there should be a minimum of 4 weeks between doses
- Moderate or severe febrile illness (temperature $\geq 39^{\circ}\text{C}$) is a temporal contraindication, and the child should not be vaccinated until improvement.
- Any condition or criteria, including acute or chronic clinically significant abnormality that in the opinion of the clinical staff might compromise the wellbeing of the volunteer

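### The survey exclusion rule permits outcome-related exclusion and replacement of children at the 6-month endpoint survey; the effect is probably small and the clause can be removed at almost no cost

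*Combined protocol and SAP*

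**What the plan says.** The last survey exclusion criterion has the same wording in the protocol synopsis, protocol 7.5.1 and SAP 3.1.1.1. It covers any acute or chronic condition that in the investigator's opinion "might compromise the wellbeing of the participant or interfere with the outcome of the study". No conditions are listed. Injury that rules out swabbing has its own criterion.

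SAP 3.1.1.1 applies the list to both surveys: "To participate in each cross-sectional surveys (baseline and post vaccination), one child per household will be randomly selected for the nasopharyngeal sampling". Protocol 7.11 puts allocation after baseline: "Following the results of the baseline survey, clusters will be randomized in a 3:3:1 ratio". The 6-month survey therefore falls after randomisation.

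Protocol 7.5.2 says of the post-vaccination survey: "In the rare event that the child is not eligible to participate another member will be randomly selected from the list". The same section has the team record the child's "recent symptoms of an upper respiratory tract infection, including receiving any antimicrobials in the previous two weeks". SAP 3.1.5 limits the primary outcome to children with a swab result.

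On blinding, protocol 7.11 states that "personnel at KWTRP will be blinded to group allocation until after the completion of culture and serotyping in each survey". It says that control villages are not blinded and that vaccination nurses must not disclose which vaccine was given. It is silent on the survey teams. In the post-vaccination survey, 7.5.2 lists the household questionnaire, which asks about vaccination in the campaign, as step 1 and selection of the child as step 2.

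SAP 4.3.1 plans a table by intervention group of screen failures with reasons in both surveys, and of reasons for swabs not taken.

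**The concern.** Both deciding comparisons treat the follow-up sample as a random sample of resident children in each arm. The outcome is VT carriage, so a rule allowing exclusion because a condition may affect the outcome is a rule allowing selection on presumed relation to carriage. At 6 months it operates after allocation. The excluded child leaves the analysis set and a substitute enters.

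The clause also fits poorly with the rest of the plan. The questionnaire records respiratory symptoms and recent antimicrobials for the selected child, which makes sense only if such children are swabbed and kept. They belong to the community whose carriage is being estimated. The parallel criterion for vaccination stops at wellbeing, and the survey's own injury and wellbeing exclusions already protect the child. The part about the outcome serves no stated purpose.

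At stake is a shift in the difference between arms if exclusions are more frequent, or fall on different children, in one arm. To a lesser degree, community prevalence is also misstated if the rule is applied alike everywhere.

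**Working it through.** **Inputs from the documents** (protocol 7.12): 27 clusters of 36 in each vaccine arm (972 children) and 9 clusters of 36 in the control arm (324); intra-cluster correlation 0.02; VT carriage 30% without vaccination and 15% after full dose; margin 7.5 points; one-sided 2.5% for non-inferiority and two-sided 5% for superiority.

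**Assumed, because the documents give neither:** q, the share of sampled children excluded and replaced under the clause in one arm only; and d, the difference in VT carriage between those children and their replacements.

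**Step 1. Reproduce the plan's power.** Design effect = 1 + (36 − 1) × 0.02 = 1.70. SE with 15% in both vaccine arms = √(2 × 0.15 × 0.85 × 1.70 / 972) = 2.11 points. Power = Φ(7.5/2.11 − 1.96) = 94.4%, which agrees with the stated minimum of 90%. The plan's figures are not in dispute; they supply the standard errors below.

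**Step 2. Size of the shift.** Shift = q × d.

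| q | d = 10 points | d = 15 points |
|---|---|---|
| 1% | 0.10 | 0.15 |
| 2% | 0.20 | 0.30 |
| 5% | 0.50 | 0.75 |

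At 1–2% the shift is 0.1–0.3 points. That is 0.7–2% of the planned 15-point difference between full dose and control, and 1.3–4% of the 7.5-point margin.

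**Step 3. Effect on error rates.**

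*Superiority*, the comparison in which survey teams can tell the arms apart. With no true effect (30% in both arms), SE = √(0.30 × 0.70 × 1.70 × (1/324 + 1/972)) = 3.83 points. Two-sided error with shift b = Φ(b/3.83 − 1.96) + Φ(−b/3.83 − 1.96).

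*Non-inferiority*, the comparison in which allocation is meant to be concealed. At the margin (15% v 22.5%), SE = √((0.15 × 0.85 + 0.225 × 0.775) × 1.70 / 972) = 2.30 points. False non-inferiority = Φ(b/2.30 − 1.96), if the excluded children are in the fractional arm and carry more than their replacements.

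| Shift b (points) | Superiority error (nominal 5%) | False non-inferiority (nominal 2.5%) |
|---|---|---|
| 0.1 | 5.0% | 2.8% |
| 0.3 | 5.1% | 3.4% |
| 0.5 | 5.2% | 4.1% |
| 0.75 | 5.4% | 5.1% |

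**Step 4. A harsher assumption.** Let 45% of the excluded children carry VT. With q = 5% in the fractional arm, the children analysed have prevalence (22.5 − 0.05 × 45)/0.95 = 21.3%. The shift is 22.5 − 21.3 = 1.2 points and false non-inferiority is 7.4%. With q = 2% the shift is 0.46 points and the error 3.9%. In the superiority comparison, q = 5% gives 0.79 points and 5.5%.

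**Step 5. Direction.** The sign of d is unknown. If the excluded children carry less than their replacements, the shifts reverse. If the same share of similar children is excluded in every arm, most of the shift cancels.

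**The case against.** The strongest case on the other side is that this is a generic catch-all phrase with a hypothetical effect. Much of that stands.

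- **Who decides.** A reader might infer that field staff who know the arm may drop children at will. The survey criterion names the investigator, whereas the vaccination criterion names clinical staff. What remains is that the plan does not say how the investigator's opinion is obtained during a household visit.
- **Whom the clause targets.** A reader might infer that it is aimed at children with respiratory infection or on antimicrobials. Nothing says so, and recording these facts points towards keeping them. The wording permits their exclusion; it does not direct it.
- **Which comparison.** A reader might set the shift against the non-inferiority margin as a serious threat. Unblinded control villages and a question about campaign vaccination separate vaccinated from control villages, not full from fractional dose. Protocol 9.9.1, where information sessions cover assignment of villages to arms, sits uneasily with 7.11, but it is too ambiguous to show that villages learn which dose they received.
- **How often.** Shares of 10–20% excluded in one arm would move the result by 1–2 points at d = 10, or 13–27% of the margin. The documents do not support such rates: they call ineligibility rare, and 20% is the plan's whole allowance for refusal and absence.
- **Existing safeguards.** Replacements are drawn at random, carriage is unknown at selection, and screen failures are tabulated by group. These limit the problem. The table would show an imbalance but not correct it, and neither replacement counts nor an analysis of replaced children is planned.
- **The remedy is partial.** An opinion-based wellbeing exclusion would remain after deletion. That is true, but it serves the child's safety and does not refer to the outcome.

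**Conclusion.** The point holds as a minor one. The text permits the investigator to exclude a child, and have the child replaced, for a reason tied to the primary outcome, at the survey that decides the trial and after randomisation. Survey teams are not stated to be blinded and can tell vaccinated from control villages.

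If ineligibility is as rare as the plan expects, the effect is small: about 0.1–0.3 points for 1–2% excluded in one arm and a 10–15 point carriage difference. It would matter only from about 5% differential exclusion, and more for non-inferiority, where concealment of dose is the main protection, than for superiority. Both q and d are assumptions, and the calculation puts all exclusions in one arm. The documents do not support a conclusion that the result is likely to be biased, or that the non-inferiority finding is in danger.

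**What to change.** 1. In the synopsis, protocol 7.5.1 and SAP 3.1.1.1, end the last survey exclusion criterion after the word *participant*. This removes the part about the study outcome and keeps the injury and wellbeing exclusions.
2. State in the SAP that children with respiratory symptoms or recent antimicrobials stay in the primary analysis.
3. Add the number of replaced children by arm to the screen-failure table in SAP 4.3.1. With that count a reader can bound the shift as q × d.
4. Add a sensitivity analysis of the primary outcome restricted to first-selected children. It cannot recover the carriage of excluded children, but it shows whether the substitutes alter the result.

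**Cost:** one phrase deleted in three places, an indicator of first-selected or replacement child if the form lacks one, and one table line. No extra swabs, visits or staff are needed. The restricted analysis loses little: with 5% of children removed, cluster size falls to 34.2 and non-inferiority power is 93.8%, against 94.4%.
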